5.4. DURATION OF TREATMENT

Patients will receive at least 2 cycles of study drug unless there is disease progression or unacceptable toxicity. After the first 6 weeks of study treatment, tumour response will be assessed : patients who respond or have stable disease will receive 2 additional cycles and will be reevaluated for tumour response. Patients with progressive disease will be removed while patients who respond or have stable disease will continue study treatment until disease progression.

In case of documented progression occurring before the first disease evaluation (6 weeks), the treatment will be discontinued and the response to treatment will be defined as early progression.

6. CONCOMITANT MEDICATIONS

All treatments given in addition to the study treatment at baseline and/or during the study are regarded as concomitant treatments and will be documented on the appropriate forms of the CRF / eCRF.

6.1. PROHIBITED TREATMENTS

6.1.1. Arms A and B

- Concomitant use of yellow fever vaccine is contraindicated due to the risk of fatal generalized vaccinal disease. Concomitant use of live attenuated vaccines is not recommended due to the risk of systemic, possible fatal disease.
- Patients must not receive any other anticancer treatment while on study.
- During the study and within 30 days following the last study drug dosing the patient will not participate in another study.
- In combination with methotrexate, the following medications are prohibited :

- phenylbutazone
- indometacine
- phenytoine
- salicylates (used at antalgic, anti-pyretic or anti-inflammatory doses)
- trimethoprim
- and probenecid

6.1.2. Arm A

Strong inhibitors of the cytochrome P450 isoform 3 A4 (CYP3A4) are prohibited during study treatment, especially ketoconazole and ritonavir. A non-exhaustive list of inducers or inhibitors of CYP3A4 is provided in Appendix 8. Concomitant use of CYP3A4 inhibitors or inducers should be avoided during the treatment period since they could alter systemic exposure to vinflunine (IRPF CSR CA 18 3009).

6.1.3. Arm B

Cross-over to vinflunine is prohibited.

6.2. RESTRICTED TREATMENT

6.2.1. Arm A

Caution is warranted when administering vinflunine to patients taking drugs that are highly dependent on CYP3A4 for metabolism and have a narrow therapeutic index. Systemic exposure to these medications could be increased while receiving vinflunine.

Even if no data is available, the opposite impact to that from inhibitors (that is decrease in vinflunine blood levels) may be anticipated. Concomitant **CYP3A4 inducers** should be avoided (list provided in Appendix 8), if possible, since they could alter the systemic exposure to vinflunine.

The use of concomitant medications that prolong the QT/QTc interval should be avoided (list provided in <http://crediblemeds.org/everyone/composite-list-all-qtdrugs/?rf=All>).

6.2.2. Arm A and B

The concomitant use of non steroidal anti-inflammatory drugs including selective inhibitors of cyclooxygenase 2 and penicillin is not recommended because those drugs can decrease the renal clearance of methotrexate.

6.3. AUTHORISED TREATMENTS

- In the two study arms :
 - ancillary treatments will be given as medically indicated: antiemetics, antidiarrhoeals, antibiotics etc
 - analgesics (if opioids are given, laxative prophylaxis should be adapted in the vinflunine arm (arm A) according to section 5.1.1.2)
 - localized palliative radiotherapy will be allowed if the irradiation concerns less than 10% of the bone marrow reserve (see Appendix 3)
 - prophylactic or therapeutic use of G-CSF will be permitted according to institutional guidelines.
 - erythropoietin according to institutional practice
 - nutritional support

7. PLAN OF THE STUDY

Written informed consent will be obtained from the patient before any study specific procedure is undertaken. Patients will be informed about the study, both verbally and by reviewing the patient information sheet and consent form. The patient must be given the opportunity to ask questions and be given time to consider his/her participation. The investigator and the patient will both sign and personally date the consent form as confirmation of consent.

Following the amendment PA11, the addendum to the informed consent will be signed by all patients (under treatment or in follow-up).

7.1. SCREENING PERIOD

The screening period is the time preceding randomization and includes the 21-day period for performing screening assessments.

Table 18: Study procedures during the screening period

Study screening procedure	Timing – Comments
Written informed consent	To be obtained and signed both by the patient and the investigator prior to any study specific procedure
Demography, medical history, diagnosis and prior therapy	To be done once at baseline
Serum or urine pregnancy test in women of childbearing potential	Test within 72 hours prior to the first study treatment.
TUMOUR ASSESSMENT - Cervical CT-Scan or MRI (1) - Chest / upper abdominal CT-Scan or MRI (1) - Other imaging if necessary (3)	Mandatory assessments are to be performed within 21 days prior to the first study treatment.
SAFETY ASSESSMENTS - Electrocardiogram - Laboratory test (2)	Within 7 days prior to first study treatment
PHYSICAL EXAMINATION Height, weight, blood pressure and pulse, temperature, performance status (WHO score)	Within 7 days prior to first study treatment
SYMPTOMS / CONCOMITANT TREATMENTS	Within 2 weeks prior to first day of treatment
Health-related QUALITY OF LIFE (EORTC QLQ-C30 and QLQ H & N 35 questionnaires)	To be obtained before randomisation (within 24 hours)

(1) Chest CT-scan must include the supraclavicular area

(2) Haematology: complete blood count. Serum chemistry: transaminases, alkaline phosphatase, total bilirubin, total protein, albumin, urea, creatinine and calculated (Cockcroft-Gault) creatinine clearance, glucose, calcium, sodium, potassium, magnesium, chloride, bicarbonate

(3) Bone scintigraphy, brain CT-scan or MRI, etc

7.2. ASSIGNMENT OF SCREENING NUMBER

For any patient screened, the site will assign a unique screening number which cannot be reused for any reason. Patient who have completed all specified baseline screening procedures and satisfy all the inclusion/exclusion criteria may be proposed for randomisation. For each site, a patient screening log is to be completed with the patient's screening number and the registration number, assigned by the randomisation if the patient is registered. If a patient is not registered, the reason for exclusion from the study will be recorded in this log.

7.3. STUDY ENTRY

Randomisation will be performed by using Interactive Voice Response System (IVRS) or Interactive Web Response System (IWRS).

Once written consent has been given by the patient, all inclusion/exclusion criteria must be checked by the investigator in order to confirm eligibility, prior to IVRS (or IWRS) randomisation procedure. The following information will be required when the investigator calls the IVRS or logs in IWRS for patient enrolment:

- study code,
- personal user access number and secret code
- institution name, investigator's name and country
- patient's birth date (day/month/year)
- answers to the questions relating to the stratification factors
- patient's eligibility.

The IVRS / IWRS will randomly assign the patient to one of the two treatment arms and will allocate the patient a registration number that will be communicated to the investigator. In parallel, the sponsor will receive this registration number as well as any information submitted by the investigator during the randomisation procedure.

The patient number will have six digits. The first two digits identify the country; the third and fourth, the centre; and the last two digits the patient within the centre. This patient registration number must be reported on all CRF pages and in any study document. A patient who has not been randomised and registered before the first administration will not be accepted for the study at a later date.

Randomisation is the starting point of the study, it is mandatory not to exceed an interval of 1 week between the date of registration and the start of the study treatment. In any case, all events occurring after registration must be recorded in the CRF /eCRF and will be taken into account in the analysis, whether the patient received the study treatment or not.

7.4. EVALUATION DURING THE STUDY PERIOD

The treatment period begins on the day of randomisation and continues until 30 days after the last study treatment administration.

The following assessments need to be completed throughout the treatment period:

Table 19: Assessments during the treatment period

Assessments	Timing - Comments
PHYSICAL EXAMINATION including weight, blood pressure and pulse, temperature, performance status (WHO score)	To be performed at day 1 of each cycle.
REVIEW OF SYMPTOMS, TOXICITY AND TREATMENTS	To be performed at day 1 of each cycle. All clinical findings and results from any complementary examination should be recorded in the CRF / eCRF.
LABORATORY TESTS (1)	
Haematology	- To be performed within 24 hours on days 1 and 8 of each cycle in arm A and before each weekly administration in arm B - In case of fever or infection according to institutional standards and investigator decision.
Serum chemistry	- To be performed within 24 hours before day 1 of each cycle in both arms (except glucose, total protein and albumin every 6 weeks)
ECG	- To be performed on D1 of the first cycle before and after drug administration in both arms and then every two cycles in both arms
TUMOUR ASSESSMENT (2)	To be performed every 6 weeks (+/- 3 working days) from randomisation (regardless of the timing of treatment cycles). All sites identified at baseline must be evaluated at each tumour assessment.
Health-related QUALITY OF LIFE (EORTC QLQ-C30 and QLQ H & N 35)	To be assessed every 6 weeks

(1) Haematology: complete blood cell count.

Serum chemistry: transaminases, alkaline phosphatase, total bilirubin, total protein, albumin, urea, creatinine and calculated (Cockcroft-Gault) creatinine clearance, glucose, calcium, sodium, potassium, magnesium, chloride, bicarbonate

(2) Tumour assessment: all target lesions (measurable disease) and non-target lesions (non-measurable disease) found at baseline should be re-investigated at each tumour assessment. Additional examinations may be performed if appearance of new lesions is suspected.

- Only the lesions found at baseline must be re-investigated. The same methods of assessment used at baseline should be used throughout the study to ensure comparability (*i.e.* scans performed immediately following bolus contrast administration using a standard volume of contrast, the identical contrast agent and preferably the same scanner).
- Lesions on chest X-rays are acceptable as measurable lesions when they are clearly defined and surrounded by aerated lung.
- Ultrasound is not an acceptable method to measure disease.
- All adverse events which occurred during the cycle must be assessed and documented using the CTCAE version 3.0.
- ECG to be performed on day 1 of cycle 1 before and after drug administration in both arms. Thereafter, ECG will be performed before drug administration every 2 cycles in both arms. After review of safety data including ECG results by the IDMC, the need for repeated ECGs before each cycle can be revised. In case of QT/QTc > 500 msec (grade 3), patients should be hospitalized for a close and continuous ECG monitoring until cardiology consultation.
- Concurrent prescriptions, blood products, palliative radiotherapy must be documented.

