
End of study
 
The end of study is the date of the last patient study treatment administration plus 30 days.
 
No follow-up visit will be performed. At the time of the amendment PA11:
 
 - Patients under treatment will stop the study at the EOT. - Patients under follow-up will stop immediately. 	

Study L00070 IN 309 F0
	

Table 1: Study flow chart

Required assessments	Screening period	Treatment period		End of treatment (f)	Follow-up (g)
	Day - 21 to - 1	Day 1 every cycle	Every 6 weeks		
Signed informed consent	X (a)				
Demographic data					
Demography/Medical History/Diagnosis	X				
Serum or urine pregnancy test in women of childbearing potential	X (j)				
Physical Examination/Vital signs/Weight	X (b)	X		X	
WHO Performance Status	X (b)	X		X	X
Safety					
Electrocardiogram (ECG)	X (m)	X (m)			
Pre-treatment events/Adverse events/SAE	X (k)	X		X	X
Complete blood cell count (l)	X (b)	X (c) (within 24 hours)		X	
Blood chemistry (d)	X (b) (e)	X	X (e)	X (e)	
Concomitant medications/Blood Products	X(k)	X		X	
Efficacy (i)					
Cervical CT-Scan or MRI	X		X	X	X (h)
Chest/upper abdominal CT-Scan or MRI	X		X	X	X (h)
Other imaging if necessary	X		X	X	X (h)
Health-related quality of life					
EORTC QLQ-C30 and QLQ-H & N 35	Before randomisation within 24h		X	X	

(a) Prior to any study procedure.

(b) Within 7 days prior to first study drug treatment.

(c) CBCC performed on days 1 and 8 in arm A; on days 1, 8 and 15 in arm B

(d) Transaminases, alkaline phosphatase, total bilirubin, urea, creatinine, calculated (Cockcroft-Gault) creatinine clearance, calcium, sodium, potassium, magnesium, chloride, bicarbonate.

(e) Glucose, total protein and albumin to be performed in addition.

(f) Within 30 days after study treatment discontinuation.

(g) Until disease progression: every 6 weeks. After disease progression, every month for the first 6 months and then every 3 months until death.

At the time of the amendment PA11, no more follow-up visit will be performed.

(h) In case of treatment discontinuation for other reason than PD, all efficacy assessments must be performed every 6 weeks from time of randomisation until disease progression is documented, then survival information will be collected approximately every month for the first 6 months then every 3 months until death.

At the time of the amendment PA11, these assessments will not be performed.

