1. INTRODUCTION

1.1. BACKGROUND ON THE STUDY

1.1.1. Background on the disease

Squamous cell carcinoma of the head and neck (SCCHN) represents 5% of newly diagnosed cancers in adult patients. Worldwide more than 500,000 new cases are projected annually and approximately 300,000 deaths are attributed to this disease.

It is a potentially curable malignancy when diagnosed at an early stage. Unfortunately, patients often present with an advanced locoregional disease. Despite aggressive local management, fewer than 30% of those patients are cured. The majority will die of locoregional recurrences. Approximately, 10% of newly diagnosed patients and up to 30% of relapsed patients will present with distant metastases. Locoregional recurrence not suitable for local therapy and metastatic disease are incurable and have been managed palliatively with chemotherapy.

Many single agents have been shown to produce tumour response including methotrexate, cisplatin, carboplatin, bleomycin, doxorubicin, taxanes, vinblastin, vinorelbine and 5-fluorouracil (5-FU) (Colevas D., 2006). Combination regimens produced statistically higher response rates than single agents (Forastiere A., 1992 ; Jacobs C., 1992). The combination of cisplatin and 5-FU emerged as a favoured treatment in the 1980s and 1990s. This was based on the higher response rates reported in recurrent/metastatic disease (Jacobs C., 1992 ; Clavel M., 1994) but at the expense of greater toxicity and without demonstrating improved survival. Triple-agent regimen, usually docetaxel, cisplatin and 5FU, was shown to be superior to cisplatin plus 5 FU but increased toxicity limits its use to induction chemotherapy (Posner M, 2007, Vermorken JB, 2007c). Cetuximab demonstrated significantly prolonged locoregional control and overall survival when used in combination with radiotherapy in locally advanced SCCHN (Bonner J.A., 2006). More recently, the addition of cetuximab to platinum-based chemotherapy improved overall survival when given as first-line treatment in patients with recurrent/metastatic SCCHN (Vermorken JB, 2008). The median overall survival was increased from 7.4 months to 10.1 months by the addition of cetuximab. However,

approximately one third of patients respond to first-line platinum-based therapy. Thus, there is clearly an unmet therapeutic need for the treatment of recurrent/metastatic SCCHN who failed platinum-based therapy.

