8.1.2.2. Criteria for evaluation

◆ **Target lesions**

The evaluation of target lesions will be performed using the sum of the diameters (longest for tumour lesions, short axis for lymph nodes) for all these lesions. If lymph nodes are to be included in the sum, then, as noted above, the short axis is added into the sum. The baseline sum diameters will be used as reference to further characterise the objective tumour response of the measurable dimension of the disease as follows :

- **Complete Response (CR)** : disappearance of all target lesions. Any pathological lymph nodes (whether target or non-target) must have reduction in short axis to < 10 mm.

- Partial Response (PR) : at least a **30% decrease** in the sum of diameters of target lesions taking as reference the baseline sum diameters.
- Progression (PD) : at least a **20% increase** in the sum of diameters of target lesions taking as reference the smallest sum on study (this includes the baseline sum if that is the smallest on study). In addition to the relative increase of 20%, the sum must also demonstrate an absolute increase of at least 5 mm. Note that the appearance of one or more lesions is also considered as a progression.
- Stable Disease (SD) : neither sufficient shrinkage to qualify for PR nor sufficient increase to qualify for PD taking as reference the smallest sum diameters while on study.

◆ **Non target lesions**

The evaluation of non-target lesions will be as follows :

- Complete Response (CR): disappearance of all non-target lesions and normalisation of tumour marker level. All lymph nodes must be non-pathological in size (< 10 mm short axis).
- Non-CR / Non-PD: persistence of one or more non-target lesion(s) and/or maintenance of tumour marker level above the normal limits.
- Progression (PD): appearance of one or more new lesions and/or unequivocal progression of existing non-target lesions such as increase in a pleural effusion from “trace” to “large”, increase in lymphangitic disease from localised to widespread.

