Sensitivity analyses of PFS will be performed in the ITT population and in the eligible population. Firstly, an analysis will be conducted in which patients who did not show evidence of PD before starting new anti cancer therapy will be censored at the date of initiation of new anti-cancer therapy. Secondly, the analysis will be repeated considering the start of new anti-cancer therapy as

an event. These two analyses aim at ruling out the bias that could arrive from the potential imbalance of further anti-cancer therapy between the two arms.

Another sensitive analysis will consider the patient in progression the day after the last tumor assessment showing no progression. For patients who progressed early or were assessed as PD at the first evaluation, they will be considered as progressing at the day after the date of randomisation. This analysis aims at ruling out potential ascertainment bias and taking into account the potential imbalance of early progressors between the two treatment arms.

A multivariate analysis using a stratified Cox proportional hazard model for Progression-Free Survival will be performed on the ITT and Eligible population with the same stratification factors as described above (see §11.5.3.2.1). The following prognostic factors will be taken into account :

- Age (< 50 years versus \geq 50 years),
- Primary tumour site (oral cavity, oropharynx, larynx, hypopharynx, nasal cavity, other),
- Extent of disease (locoregional recurrence versus metastatic disease with or without locoregional recurrence,
- Tumour grade (well or moderately differentiated, poorly differentiated).

In case of missing data in some covariates of the multivariate analysis, in addition of the complete case analysis (listwise selection approach) consisting in omit those cases with missing data and to run the analysis on what remains, a multiple imputation based approach where complete data sets are drawn will be used to perform the multivariate analysis. The imputation model will be defined in the SAP.

11.5.3.2.4.3. Tumour response

The analyses of tumour response will be performed on the ITT population and on the population evaluable for response in the two treatment arms.

❖ Objective Response and Disease Control Rate

Objective Response Rate and Disease Control Rate in each treatment arm will be estimated and presented along with a corresponding 95% confidence interval. The ORR and DCR will be

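### Table 19 requires re-imaging only of baseline lesions, while the flow chart schedules chest/upper abdominal scans every 6 weeks, so silent new distant lesions can be found late or missed in PFS and disease control

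*Protocol*

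**What the plan says.** **Table 1 (flow chart).** The row "Chest/upper abdominal CT-Scan or MRI" is marked at screening, every 6 weeks on treatment, at end of treatment and in follow-up. The cervical row is marked in the same way. Only the row for other imaging is conditional on need. The heading of this block carries a footnote marker (i) whose text is not visible in the copy available for review.

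**Protocol 7.1, Table 18.** Cervical and chest/upper abdominal imaging is compulsory for everyone at baseline: "Mandatory assessments are to be performed within 21 days prior to the first study treatment".

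**Protocol 7.4, Table 19 and its notes.** The row says "All sites identified at baseline must be evaluated at each tumour assessment". The notes add "Only the lesions found at baseline must be re-investigated" and, for anything else, "Additional examinations may be performed if appearance of new lesions is suspected".

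**Protocol 7.5, Table 20.** It repeats the baseline-sites wording. Its note 4 allows for further examination if new lesions are suspected.

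**Protocol 8.1.2.2 and 8.1.2.3.** On target lesions: "Note that the appearance of one or more lesions is also considered as a progression". In Tables 21 and 22 every category other than progression, including not evaluable, requires that no new lesion is present. Neither table has an entry for a region that was not imaged.

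**Population.** Locoregional-only recurrence is part of the trial. A prognostic factor in Protocol 11.5.3.2.4 contrasts "locoregional recurrence versus metastatic disease with or without locoregional recurrence".

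**The concern.** The two tables give a site different instructions for the same visit. Under Table 1 a patient with disease only in the neck has a chest/upper abdominal scan every 6 weeks. Under Table 19 that patient has a clean baseline chest scan which need never be repeated unless the investigator suspects something. The response tables then accept the absence of new lesions, and the patient is classed as stable or responding with a progression-free date.

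The error runs one way. A new lesion that is not looked for can only lengthen observed PFS and duration of disease control, and can only move a patient from progression to disease control. Sites that follow Table 1 and sites that follow Table 19 would also be measuring progression with different intensity. The trial is open-label, so the optional extra scan depends on an investigator who knows the treatment.

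**Working it through.** **1. The two instructions for one patient.** Take a patient with a neck recurrence and no chest lesion at baseline.

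| Step | Table 1 | Table 19 |
|---|---|---|
| Baseline chest/upper abdomen | Scanned | Scanned (Table 18) |
| Week 6, 12, ... neck | Scanned | Scanned |
| Week 6, 12, ... chest/upper abdomen | Scanned | Only if new lesions are suspected |
| Silent lung lesion at week 6 | Seen, so PD | Not seen; can be recorded as SD |

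**2. Later rules do not catch it.** SAP 4.2.1 censors PFS at the later of the last tumour assessment and the last follow-up contact showing no progression, with no condition on the regions imaged. The evaluability conditions for the interim analysis (Protocol 11.5.6.2) ask that baseline target or non-target lesions be assessed; they do not ask for a search elsewhere. Protocol 11.5.3.2.4.2 planned a PFS sensitivity analysis against ascertainment bias, but SAP 10.4.1 contains only the primary PFS analysis.

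**3. Delay per missed scan.** 6 weeks = 42/30.4375 = 1.38 months (month length from SAP Appendix 2). Protocol Table 2 puts median PFS on methotrexate at 1.5-2.0 months.

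**4. Illustration for median PFS.** Assumptions, not in the documents: exponential PFS with true median 2.0 months, so λ = ln 2/2.0 = 0.3466 per month; a share s of patients whose first progression is a silent new lesion; detection late by d months. The observed median m solves

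(1 − s)·exp(−λm) + s·min{1, exp(−λ(m − d))} = 0.5.

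For s = 0.10 and d = 1.38: exp(0.478) = 1.613, the bracket is 0.9 + 0.161 = 1.061, and m = ln(2 × 1.061)/0.3466 = 2.17 months.

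| s | One scan late | Two scans late |
|---|---|---|
| 5% | 2.09 | 2.16 |
| 10% | 2.17 | 2.34 |
| 20% | 2.33 | 2.80 |

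The model lets the whole delay run, with no symptoms, neck progression or death in between, so for a given s it leans high.

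**5. Interim rule.** The plan's interval reproduces: 0.61 ± 1.96·√(0.61 × 0.39/100) = 0.514 to 0.706, against [51%-71%] stated. The rule stops the study at 49 or more progressions in 100. With X ~ Binomial(100, 1 − observed non-progression rate), P(X ≥ 49) is:

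| True non-progression rate | No inflation | +2 points | +5 points | +10 points |
|---|---|---|---|---|
| 45% | 0.90 | 0.82 | 0.62 | 0.24 |
| 51% | 0.54 | 0.38 | 0.18 | 0.03 |

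The inflation values are assumed. The rule uses the test arm alone, so no control-arm comparison offsets the effect.

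**6. Overall survival.** Deaths do not depend on imaging. The planned 437 deaths, the expected 325 and their power are not touched.

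**The case against.** The strongest reply is that Table 19 sets a minimum and forbids nothing. Sites also had Table 1. SAP section 4 and Protocol 7.7 speak of all lesions without limiting them to baseline. Patients are examined on day 1 of each 3-week cycle, so symptomatic spread would prompt a scan. The hidden footnote (i) might qualify the imaging rows. Secondary efficacy is called descriptive (Protocol 11.5.1, SAP 3), and the wording is the same in both arms.

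Much of this stands as a limit on size, but it does not remove the conflict. Optional imaging on suspicion does not find silent lesions. If footnote (i) narrowed Table 1 to baseline lesions, the contradiction would shrink but the gap in searching for new lesions would be confirmed. The secondary analyses are labelled descriptive, yet SAP 10.4.1.1, 10.4.2.1 and 10.4.2.2 still compute stratified log-rank and CMH comparisons.

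Three stronger readings are not supported:

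- A reader might take the background statement that "up to 30% of relapsed patients will present with distant metastases" to mean that most trial patients have no chest lesion to re-image. It describes relapsed patients in general. This trial enrols patients after platinum failure, including some metastatic at diagnosis, and does not state its locoregional-only share.
- A reader might apply an assumed 10-20% to all 459 patients and count 46 to 92 as exposed. That would include patients with baseline chest lesions, who are re-imaged under either table, and patients with no observed progression.
- A reader might treat 1.4 months as a minimum delay. Symptoms, neck progression or death can end PFS sooner.

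**Conclusion.** The conflict between Table 1 and Tables 19 and 20 is in the current text and needs to be reconciled. Followed as written, Table 19 allows silent distant progression to be found about 1.4 months late per missed scan, unless symptoms prompt imaging, or to be missed. The direction is certain: longer observed PFS and duration of disease control, and higher DCR. DCR moves only through CR, PR and SD, because patients with non-measurable disease only who are non-CR/non-PD are not counted in it.

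The size is not derivable from the documents. Under the assumptions shown, a 2.0-month median PFS gains about 0.1 to 0.8 months. How many sites followed Table 19, and what was recorded for regions not imaged, is unknown because the tumour assessment form is not included.

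It would go too far to infer that PFS or disease control is in fact overstated, or that the comparison between arms is biased. Differential suspicion is possible in an open-label trial but not shown. Nor do the documents show that the week-6 interim result was wrong. Recruitment was later stopped after a futility analysis of overall survival, which does not rest on imaging.

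**What to change.** **Protocol.** Delete the sentence limiting re-investigation to baseline lesions, and align Tables 19 and 20 with the cervical and chest/upper abdominal imaging in Table 1, after checking footnote (i). Recruitment is closed and amendment PA11 ended follow-up, so this helps only patients still on treatment and cannot recover scans already missed.

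**SAP.** Keep the primary PFS and DCR definitions and add:

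- A table by arm of the number of non-PD tumour assessments without both cervical and chest/upper abdominal imaging.
- A sensitivity analysis of PFS and DCR in which such assessments do not establish absence of progression. Documented progressions and deaths stay as events. Other patients are censored at the last assessment with both regions imaged, or at randomisation if there is none. The last-contact clause in SAP 4.2.1 must follow the same rule; otherwise a later contact would restore the progression-free date. For DCR, disease control resting only on incomplete assessments counts as not evaluable.

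This should not replace the primary analysis. Progression on an incomplete scan still counts while disease control does not, and not-evaluable patients stay in the denominator, so DCR is pushed down one-sidedly.

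**Cost.** A little more analysis work, and earlier censoring and a lower DCR in the sensitivity analysis. No new scans are needed for the SAP part. It assumes that the tumour assessment data (SAP Appendix 1, listings 16.2.6) identify the regions imaged at each visit.
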